3.1.3 Long-Term Follow-Up Period

A long-term follow-up period will start after the EOT/Early Termination (ET) Visit. Follow-up will continue for a maximum of 12 months. All patients without disease progression will be monitored every 8 weeks to evaluate PFS for a maximum of 12 months or until disease progression, death, or consent is withdrawn, whichever occurs first.

The bi-monthly visits will consist of imaging to evaluate disease status, performance status evaluation using the Eastern Cooperative Oncology Group performance status (ECOG PS), and assessment for any post-investigational treatment. Other changes in medical history or concomitant medications and AEs will be assessed. Imaging to evaluate disease status will begin 8 weeks after the last diagnostic CT scan or brain MRI performed during the study treatment period. Diagnostic CT scan will be performed in all patients. Brain MRI will only be performed in patients with known brain metastases. Patients with extracranial lesions will be evaluated for progression using RECIST version 1.1. Patients with brain metastases without extracranial lesions will be evaluated for progression using RANO-BM. Patients with extracranial lesions and brain metastases will be evaluated for progression using both RECIST version 1.1 (extracranial lesions) and RANO-BM (brain metastases). Additional details are provided in the Imaging Review Charter.

As long as there is no disease progression, imaging to evaluate disease status will be performed every 8 weeks.

For patients with disease progression or starting alternative anticancer therapy, imaging to evaluate disease status will be performed according to the local site standard of care. Review of images at this point will be done locally and not by the central imaging core laboratory. Additionally, those patients will no longer be followed every 8 weeks, but every 12 weeks, to assess survival, disease status, and post-progression therapy. Follow-up contacts (by clinic visits or telephone call) will be performed every 12 weeks until death, lost to follow-up, study end (12 months post-last patient EOT/ET Visit), or study termination by the Sponsor, whichever occurs first.

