2.2 Secondary Objectives

The secondary objectives are as follows:

- To assess the CB of CAM-H2 by evaluating the proportion of patients with a CR, PR, and SD in the dose escalation phase;
- To assess duration of response (DoR);
- To evaluate progression-free survival (PFS) from the time of enrollment in the study to progression of disease or death;
- To measure median OS;
- To evaluate intra- and inter-patient dosimetry and PD of CAM-H2 (dose escalation phase only); and
- To assess for the development of anti-drug antibodies (ADAs).

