6.5 Long-Term Follow-Up Period and End of Study

A long-term follow-up period will start after the EOT/ET Visit. Follow-up will continue for a maximum of 12 months. All patients without disease progression will be monitored every 8 weeks to evaluate PFS for a maximum of 12 months or until disease progression, death, or consent is withdrawn, whichever occurs first.

The bi-monthly visits will consist of imaging to evaluate disease status, performance status evaluation using ECOG PS, and assessment for any post-investigational treatment. Other changes in medical history or concomitant medications and AEs will be assessed. Imaging to evaluate

disease status will begin 8 weeks after the last diagnostic CT scan or brain MRI performed during the study treatment period. Diagnostic CT scan will be performed in all patients. Brain MRI will only be performed in patients with known brain metastases. Patients with extracranial lesions will be evaluated for progression using RECIST version 1.1. Patients with brain metastases without extracranial lesions will be evaluated for progression using RANO-BM. Patients with extracranial lesions and brain metastases will be evaluated for progression using both RECIST version 1.1 (extracranial lesions) and RANO-BM (brain metastases). Additional details are provided in the Imaging Review Charter. As long as there is no disease progression, imaging to evaluate disease status will be performed every 8 weeks.

For patients with disease progression or starting alternative anticancer therapy, imaging to evaluate disease status will be performed according to the local site standard of care. Review of images at this point will be done locally and not by the central imaging core laboratory. Additionally, those patients will no longer be followed every 8 weeks, but every 12 weeks, to assess survival, disease status, and post-progression therapy. Follow-up contacts (by clinic visits or telephone call) will be performed every 12 weeks until death, lost to follow-up, study end (12 months post-last patient EOT/ET Visit), or study termination by the Sponsor, whichever occurs first.

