- d. If the patient has CB and the cumulative kidney dose remains <23 Gy (based on the dosimetry results during Cycle 1), the patient will not undergo an EOT Visit but proceed to the next cycle's eligibility assessment visit (Table 8). If the patient does not have CB, the patient will undergo an EOT Visit and no further treatment will be administered. The patient will enter the LT FU period.

- e. An LT FU period will start after the EOT (or ET) Visit. Follow-up will continue for a maximum of 12 months as described in [Sections 3.1.3](#) and [6.5](#). Imaging to evaluate disease status will begin 8 weeks after the last diagnostic CT scan or brain MRI performed during the study treatment period. As long as there is no disease progression, imaging to evaluate disease status will be performed every 8 weeks. For patients with disease progression or starting alternative anticancer therapy, imaging to evaluate disease status will be performed according to the local site standard of care. Additionally, those patients will no longer be followed every 8 weeks, but every 12 weeks, to assess survival, disease status, and post-progression therapy.
- f. Medical history should include confirmation of lesion size.
- g. Prior and concomitant meds should include information on any thyroid-blocking drugs.
- h. Acceptable thyroid-blocking drugs include potassium iodate capsules, potassium iodide capsules, Lugol's 1% solution, and potassium perchlorate capsules (see [Section 5.2.5.1](#)). Patients will not always take the thyroid-blocking drugs (potassium iodide 130 mg daily or equivalent) on the same day that they are delivered, but will take them starting 24 hours before study drug administration, 1 hour before study drug administration, and 24 and 48 hours after study drug administration as indicated.
- i. If the patient is discharged prior to 48 hours, deliver the thyroid-blocking drugs for 48 hours at 24 hours. Patients will still take the thyroid-blocking drugs 48 hours after study drug administration.
- j. Delivery of thyroid-blocking drugs at this visit will occur only for patients eligible for and continuing to Cycle 2.
- k. Confirmation of ingestion of thyroid-blocking drugs will be performed by directly asking the patient and by counting pills left in his/her medication bottle.

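### Survival follow-up is written two incompatible ways; depending on which rule is applied, late OS is biased downward or OS cannot be estimated beyond about 17.5 months

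*Combined protocol and SAP*

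**What the plan says.** Section 3.1.3, repeated in the synopsis and Section 6.5, contains three statements about the period after the EOT/ET visit.

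- **A general limit.** As worded in Section 6.5: "Follow-up will continue for a maximum of 12 months". No subgroup is named. The Appendix A footnotes to Tables 7 to 10 repeat it ("Follow-up will continue for a maximum of 12 months as described in" Sections 3.1.3 and 6.5).
- **Patients without progression.** "All patients without disease progression will be monitored every 8 weeks to evaluate PFS for a maximum of 12 months", or until progression, death or withdrawal of consent. No later survival contact is stated for them.
- **Patients who progress or start other anticancer therapy.** "those patients will no longer be followed every 8 weeks, but every 12 weeks, to assess survival, disease status, and post-progression therapy". Clinic or telephone contacts continue until death, loss to follow-up, "study end (12 months post-last patient EOT/ET Visit), or study termination by the Sponsor, whichever occurs first".

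Section 10.3 gives the same definition of study end. Section 2.2 lists the objective "To measure median OS", and Section 7.2 lists OS as a secondary efficacy endpoint. Section 9.2.1 names ORR, CBR, DoR and PFS for analysis but gives no OS estimator or censoring rule. Section 9.2.4 leaves the exact statistical approach to the SAP, and the file contains no SAP text on OS.

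**The concern.** The general limit and the study-end rule cannot both hold. A patient enrolled early who progresses is due survival contacts until 12 months after the last patient's EOT/ET, which may be years after that patient's own EOT. The general sentence stops that patient at 12 months.

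If sites follow the more detailed two-stream text, whether a patient is still observed for death late in the study depends on whether the disease has progressed. Kaplan-Meier treats censored patients as having the same future risk as those who remain. Here the censored patients are progression-free and the remaining ones mostly are not, so the late curve falls too fast. The distortion grows with the share of patients with durable disease control, so it costs the drug most if it works.

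If sites follow the general limit, everyone stops at the same point after EOT and there is no such selection by progression status. The cost is that OS information ends early, possibly before the median is reached.

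Either way, deaths that were never collected cannot be recovered at the analysis stage.

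**Working it through.** The documents give no OS figure, event count or accrual time, so there is no plan figure to reproduce. The check has three parts.

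**1. When the 12-month limit falls, counted from first dose.** Inputs: EOT at Week 11 of the last cycle; the next cycle starts 2 weeks after the eligibility visit (Section 3.1); at most 2 cycles in expansion and 4 in escalation. One month is 4.35 weeks.

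- One cycle: 11 weeks = 2.5 months; limit at 2.5 + 12 = 14.5 months.
- Two cycles: 11 + 2 + 11 = 24 weeks = 5.5 months; limit at 17.5 months.
- Four cycles (escalation): 11 + 3 × 13 = 50 weeks = 11.5 months; limit at 23.5 months.

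Early termination brings the limit forward.

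**2. Why censoring by progression status matters.** Assume exponential times, with mean = median / ln 2. With median PFS 6 and median post-progression survival 10 months, a patient still progression-free at the limit has expected remaining survival (6 + 10) / 0.693 = 23.1 months. A patient who has already progressed has 10 / 0.693 = 14.4 months. The two-stream rule removes the first kind of patient from the risk set and keeps the second.

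**3. Size, by simulation.** Assumptions not in the documents: exponential time to progression and post-progression survival; no death before progression; uniform accrual over 24 months; a second cycle for everyone progression-free at Week 8; Kaplan-Meier with censoring at last contact. EOT timing is as in part 1. Three rules were compared: two-stream, general limit for all, and survival follow-up of all patients to study end.

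| Median PFS / post-progression survival (months) | Progression-free at limit | Median OS: true | Median OS: two-stream | 24-month OS: true | 24-month OS: two-stream |
|---|---|---|---|---|---|
| 6 / 10 | 13% | 19.1 | 18.7 | 38.0% | 34.7% |
| 8 / 12 | 22% | 24.0 | 22.1 | 50.0% | 44.8% |
| 10 / 12 | 30% | 26.5 | 23.2 | 55.3% | 47.9% |

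Shortfall in median OS: 0.4, 1.9 and 3.3 months. Shortfall in 24-month OS: 3.3, 5.2 and 7.4 points.

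Scenarios with shorter survival, same assumptions, two-stream against true median OS: 10.6 against 10.6 (3 / 6), 15.2 against 15.2 (4 / 9), and 17.9 against 18.0 (6 / 9). Accrual over 36 months gives nearly the same bias.

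*General limit for all.* No downward bias. The expansion-phase curve has nobody at risk after about 17.5 months, so in the 6 / 9 scenario (true median 18.0) and in all three rows of the table the median is not reached.

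*All followed to study end.* Kaplan-Meier matches true OS within about 0.1 percentage point in every scenario.

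**The case against.** The strongest counter-argument is that a downward bias can be asserted only by choosing one of two contradictory rules. A reader might infer from the two-stream paragraph that late OS will be biased downward, full stop. The documents do not support that. The unrestricted 12-month sentence appears in the same paragraph and is repeated in the footnotes; if it governs, progressed patients stop too and the mechanism disappears. This objection stands, and the conclusion is conditional for that reason. It does not rescue the plan, because the other reading loses OS beyond about 17.5 months and cuts short the contacts the protocol promises until study end.

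Other objections also have force:

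- **Population.** PFS and OS values are assumed. Patients are refractory, and the required life expectancy is only more than 6 months. With true median OS of about 18 months or less, the median is almost untouched.
- **Precision.** OS is a secondary endpoint in an uncontrolled study of 52 expansion patients with no formal sample size calculation. If about 35 deaths are observed (an assumption), the 95% interval around a 19-month median is 19 ÷ 1.39 to 19 × 1.39, about 14 to 26 months, where 1.39 = exp(1.96 / √35). Sampling error dwarfs a 0.4-month shift. It does not dwarf the loss of the median altogether, and a systematic error is worth removing when removal is cheap.
- **Numbers affected.** At median PFS 6 months about 13% of patients, 0.13 × 52 ≈ 7, reach the limit progression-free. For the last patients enrolled, the limit and study end nearly coincide. Progression-free patients who start other therapy do enter the survival stream.
- **Estimator.** Kaplan-Meier is presumed, since the documents name no OS method. It is the usual choice for a median.

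A reader might also infer that PFS and DoR are biased. They are not, by this mechanism: the end of scheduled imaging truncates them, which limits late information but does not select by prognosis.

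**Conclusion.** The inconsistency is certain from the text: the general 12-month limit conflicts with survival contacts to study end, and no survival contact is stated for patients still progression-free at 12 months after EOT/ET. Its consequence depends on which sentence sites apply.

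- **Two-stream rule.** OS censoring depends on prognosis, and Kaplan-Meier OS is biased downward from about 14.5 months after first dose for patients with one cycle and about 17.5 months for those with two. Median OS is about 0.4 to 3.3 months too low and 24-month OS about 3 to 7 points too low when median PFS is 6 to 10 months and true median OS 19 to 27 months. The effect on the median is almost nil when true median OS is about 18 months or less.
- **General limit.** No downward bias, but expansion-phase OS cannot be estimated beyond about 17.5 months.

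The magnitudes rest on exponential times, 24-month accrual, no death before progression and a Kaplan-Meier estimator, none of which the documents state. The direction under the two-stream rule needs only that progression-free patients have a better outlook than progressed ones.

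**What to change.** Reconcile the passages into one survival rule for every treated patient: a contact every 12 weeks, by telephone if preferred, until death, loss to follow-up or study end, regardless of progression status. Limit the 12-month cap to study imaging and PFS visits. Make the change in the synopsis, Sections 3.1.3 and 6.5, and the Appendix A footnotes to Tables 7 to 10. State the OS estimator and censoring rule in the SAP.

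The cost is a few extra telephone contacts, mainly for earlier-enrolled patients still progression-free at 12 months; no scan or clinic visit is added. The amendment should take effect before the first patients reach the 12-month point, since survival status not collected then may not be recoverable.

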3.1.4 Dose Escalation Rules and Dose Staggering Approach

Dose staggering will be applied for all cohorts during dose escalation. The first dose of the first patient will be administered at least 2 weeks before the first dose of the remainder of the cohort. After the review of AEs, dosimetry reports, vital signs, and electrocardiograms (ECGs) collected over 2 weeks, the remaining 2 patients of the cohort may receive the same dose level. Following completion of the initial safety assessments for the sentinel patient, the decision to proceed with the remaining patients in that cohort will be discussed and mutually agreed upon between the Investigator (or his/her designee) and the Sponsor. The decision of whether to escalate to the next dose will be formally confirmed by the Sponsor.

The proposed minimum 2 weeks between the sentinel patient and the remainder of the cohort is deemed sufficient as each dose of the cycle is a single IV administration, and it is expected that the most severe and acute reactions will occur during or soon after the infusion. Based on animal studies, potential side effects are expected to be related to high activity levels in the kidneys, that will decline rapidly after ending the IV infusion.

At each dose level, after completion of 1 cycle (2 doses) of CAM-H2 administration in at least 3 patients, each Investigator will provide a comprehensive Investigator Safety Report for his/her patients including (but not limited to) the following content:

- Relevant information on patients' demographics, characteristics, medical history, physical examination, and concomitant medications;
- List of all AEs, including severity, time of onset related to study drug administration, and duration, clearly highlighting serious adverse events (SAEs) and relatedness and causality of all AEs;
- Any clinically significant out of range clinical laboratory test results (as assessed by the Investigator);
- Neurological examination results including clinical significance for abnormal findings;
- ECG and vital sign results including clinically significant abnormal values; and
- Statement of the Principal Investigator's recommendation regarding dose decision.

Escalation to the next higher dose will only take place after review of the Investigator Safety Reports from the previous dose levels by the respective Investigators, in consultation with the Sponsor's representative (called hereafter the Safety Review Committee [SRC]). Dose escalation

will be based on dosimetry and emerging safety and tolerability data as defined by AEs, laboratory results, ECGs, and vital signs. Other parameters of interest will be considered ad hoc.

3.1.4.1 Definition of dose-limiting toxicities

DLTs are defined as toxicities occurring **only** within Cycle 1 (ie, the approximately 12-week [84-day] period that includes 2 administrations of the study drug given 4 weeks apart [including the 4-week Safety Follow-Up Period after Dose 1]). DLTs include ≥ 1 of the following:

- Study drug-related SAE in at least 1 patient in 1 cohort;
- Severe study drug-related AE in at least 2 patients in 1 cohort;
- Any death not clearly due to the underlying disease or extraneous causes;
- Development of severe renal failure (estimated glomerular filtration rate [eGFR] <30 mL/min) or a drop of >40 mL/minute in eGFR;
- Any seizure activity that is considered to be study drug-related;
- Grade 3+ thrombocytopenia with bleeding;
- Recurrent (defined in this study as occurring after >1 dose of CAM-H2 during Cycle 1) Grade 3 or 4 thrombocytopenia;
- Grade 4+ neutropenia or thrombocytopenia >7 days;
- Recurrent (defined in this study as occurring after >1 dose of CAM-H2 during Cycle 1) Grade 3 or 4 anemia and/or neutropenia;
- Recurrent (defined in this study as occurring after >1 dose of CAM-H2 during Cycle 1) Grade 3 or 4 non-hematological toxicities as listed in the Common Terminology Criteria for Adverse Events (CTCAE) version 5.0;
- An alanine aminotransferase (ALT) or aspartate aminotransferase (AST) $>3 \times$ upper limit of normal (ULN) accompanied by a total bilirubin of $>2 \times$ ULN (Hys Law);
- Grade 3 or 4 fatigue for >1 week;
- Grade 3 or 4 electrolyte abnormalities that last >72 hours or any Grade 3 or 4 electrolyte abnormalities associated with clinical signs and symptoms of any duration;
- For patients with hepatic metastases, AST or ALT $>8 \times$ ULN or AST or ALT $>5 \times$ ULN for ≥ 14 days;
- An absorbed dose to the kidneys >23 Gy;
- An absorbed dose to the bone marrow >2 Gy; or
- Other clinically significant changes in vital signs, clinical laboratory tests, ECGs, or other safety parameters deemed as a significant safety concern by the Investigator.

All AEs of the specified grades will count as DLTs, except those that are clearly and incontrovertibly due to disease progression or extraneous causes.

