Staggered dosing will be applied for all cohorts during dose escalation. The first dose of the first patient of each cohort will be administered at least 2 weeks before the first dose of the next 2 patients (sentinel dosing). Once the MTD or RDP2 has been established, 3 additional patients will be enrolled to receive the MTD or RDP2. The patients treated at the MTD or RDP2 in the dose escalation phase will be included in the readout for efficacy. The dose escalation will be done via increases of the nominal activity of CAM-H2 in cohorts of 3 to 6 patients until approximately 15 (or a maximum of 18) patients have been dosed. The actual dose levels administered to the patient can have a tolerance window of $\pm 10\%$ of the prescribed nominal activity.

Dose escalation will be decided based on a review of all the available safety data obtained after completion of Cycle 1 (ie, after 2 IV administrations) of each dose level. If a patient is not able to complete a full cycle due to AEs related to study drug administration, he/she will not be replaced, and the dose escalation rules will be followed.

In the instance that a patient is not able to complete a full cycle due to AEs not related to study drug administration or due to a negative PD distribution scan, he/she will be replaced to ensure safety data spanning a full treatment cycle can be considered for dose escalation.

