3.1.4.2 Dose escalation rules

DLTs will determine the progression/escalation with the following rules:

- If 0 out of 3 patients experience a DLT, all patients will proceed to the next higher dose level;
- If 1 out of 3 patients experiences a DLT, the same dose will be given to 3 new patients:
 - If 0 of the 3 new patients experience a DLT, all patients will proceed to the next higher dose level; and/or
 - If 1 or more of the 3 new patients experiences a DLT (≥ 2 of the 6 patients) this dose will become the MTD + 1.
- If ≥ 2 out of 3 patients experience a DLT, the MTD has been exceeded and a lower dose should be tested between this dose and the previous dose level;
- Once the MTD + 1 has been established, 3 additional patients will be exposed to the dose below the MTD + 1; and
- If the MTD + 1 is not reached, 3 additional patients will be exposed to the highest dose.

Within the planned dose range, a dose lower than the next planned dose may also be tested, depending on emerging safety, tolerability, and/or other relevant data, such as dosimetry or PD. If the highest planned dose level is found to be safe and tolerable, also considering the PD data, additional higher doses may be added by amendment.

A period of at least 4 weeks will be maintained between 2 consecutive cohorts.

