3.1.5.2 Dose modifications

The following dose modifications will be implemented in case of toxicities:

- Grade 2, 3, or 4 thrombocytopenia:
 - Withhold dosing until resolution to Grade 0 or 1;
 - Resume CAM-H2 at 50% with complete or partial resolution;
 - If a reduced dose does not result in Grade 2, 3, or 4 thrombocytopenia, administer CAM-H2 at the full planned dose for next cycle.
 - Permanently discontinue CAM-H2 for Grade 2 or higher thrombocytopenia requiring a treatment delay of 12 weeks or longer; and
 - Permanently discontinue CAM-H2 for recurrent (defined in this study as occurring after >1 dose of CAM-H2 during Cycle 1) Grade 2, 3, or 4 thrombocytopenia.
- Grade 3 or 4 anemia and neutropenia:
 - Withhold dosing until resolution to Grade 0, 1, or 2;
 - Resume CAM-H2 at 50% in patients with complete or partial resolution;
 - If a reduced dose does not result in Grade 3 or 4 anemia or neutropenia, administer CAM-H2 at full planned dose for next cycle.
 - Permanently discontinue CAM-H2 for Grade 3 or higher anemia or neutropenia requiring a treatment delay of 12 weeks or longer; and
 - Permanently discontinue CAM-H2 for recurrent (defined in this study as occurring after >1 dose of CAM-H2 during Cycle 1) Grade 3 or 4 anemia or neutropenia.
- Renal toxicity (defined as an eGFR <40 mL/minute or a 40% decrease in baseline eGFR):
 - Withhold dosing until resolution to at least 80% of baseline eGFR;
 - Resume CAM-H2 at 50% in patients with complete or partial resolution;
 - If a reduced dose does not result in another decrease of eGFR, administer CAM-H2 at the full, planned dose for next cycle.
 - Permanently discontinue CAM-H2 for eGFR decreases requiring a treatment delay of 12 weeks or longer; and
 - Permanently discontinue CAM-H2 for recurrent (defined in this study as occurring after >1 dose of CAM-H2 during Cycle 1) toxicity.

- Hepatic toxicity (Hy's Law cases):
 - Withhold dosing until resolution to ALT and AST values $<2 \times$ baseline and total bilirubin values of $<1.5 \times$ ULN;
 - Resume CAM-H2 at 50% in patients with complete or partial resolution;
 - If a reduced dose does not result in another transaminase or total bilirubin increase, administer CAM-H2 at full planned dose for next cycle.
 - Permanently discontinue CAM-H2 for transaminase or total bilirubin decreases requiring a treatment delay of 12 weeks or longer; and

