 - Permanently discontinue CAM-H2 for recurrent (defined in this study as occurring after >1 dose of CAM-H2 during Cycle 1) toxicity.
- Hepatic toxicity (patients with hepatic metastases and AST or ALT $>8 \times$ ULN or AST or ALT $>5 \times$ ULN for ≥ 14 days):
 - Withhold dosing until resolution to ALT and AST values of $<1.2 \times$ baseline and total bilirubin values of $<1.5 \times$ ULN;
 - Resume CAM-H2 at 50% in patients with complete or partial resolution;
 - If a reduced dose does not result in another transaminase or total bilirubin increase, administer CAM-H2 at full planned dose for next cycle.
 - Permanently discontinue CAM-H2 for transaminase or total bilirubin decreases requiring a treatment delay of 12 weeks or longer; and
 - Permanently discontinue for recurrent (defined in this study as occurring after >1 dose of CAM-H2 during Cycle 1) toxicity.
- Grade 3 or 4 non-hematological toxicities as listed in the CTCAE version 5.0:
 - Withhold dosing until resolution to Grade 0, 1, or 2;
 - Resume CAM-H2 at 50% in patients with complete or partial resolution;
 - If a reduced dose does not result in Grade 3 or 4 toxicity, administer CAM-H2 at full planned dose for next cycle.
 - Permanently discontinue CAM-H2 for Grade 3 or higher toxicity requiring a treatment delay of 12 weeks or longer; and
 - Permanently discontinue for recurrent (defined in this study as occurring after >1 dose of CAM-H2 during Cycle 1) Grade 3 or 4 toxicities.

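### A patient whose Cycle 1 Dose 2 is halved for related toxicity can be counted as DLT-free at the full dose level

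*Combined protocol and SAP*

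**What the plan says.** The escalation phase is a 3+3 judged on Cycle 1, which is two doses four weeks apart. These parts of the protocol bear on the point.

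- **DLT list (Section 3.1.4.1).** Grade 3/4 thrombocytopenia, anemia/neutropenia and non-hematological toxicity each carry a recurrence condition. For platelets it is "Recurrent (defined in this study as occurring after >1 dose of CAM-H2 during Cycle 1) Grade 3 or 4 thrombocytopenia". The eGFR item is "Development of severe renal failure (estimated glomerular filtration rate [eGFR] <30 mL/min) or a drop of >40 mL/minute in eGFR". Severe related events enter through "Severe study drug-related AE in at least 2 patients in 1 cohort". A related SAE in one patient is a DLT, and a final item lets the Investigator declare other significant changes as DLTs.
- **Dose modification (Section 3.1.5.2).** Dosing is withheld at Grade 2 or worse thrombocytopenia, at Grade 3/4 anemia, neutropenia or non-hematological toxicity, and for defined renal and hepatic toxicity. The renal trigger is "Renal toxicity (defined as an eGFR <40 mL/minute or a 40% decrease in baseline eGFR"; the instruction is then "Withhold dosing until resolution to at least 80% of baseline eGFR", followed by "Resume CAM-H2 at 50% in patients with complete or partial resolution".
- **Counting (Section 3.1.4.2).** With 0 of 3 the study escalates. "If 1 out of 3 patients experiences a DLT, the same dose will be given to 3 new patients".
- **Incomplete Cycle 1 (Section 3.1.1.2).** If the cause is a related AE, "he/she will not be replaced, and the dose escalation rules will be followed".
- **Review timing.** Section 3.1.4 asks for Investigator Safety Reports once at least 3 patients have had one cycle, specified as two doses. Section 3.1.5.1 has the Safety Review Committee (SRC) meet once at least 3 patients have had a full treatment cycle.
- **Analysis sets (Section 9.1).** Only the SAF and FAS are defined, both requiring at least one dose. There is no DLT-evaluable set.

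**The concern.** A 3+3 count is informative about a dose level only if the patients counted as free of DLT received that level, or if failing to receive it because of toxicity is itself counted. Here the toxicity that leads to a halved Dose 2 is often not a DLT, because it must recur first. The halving then makes recurrence less likely, so the DLT condition is tested at lower activity than the level being judged.

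Determining DLT, MTD and RDP2 is part of the primary objective of the escalation phase (Section 2.1), and at least 52 patients are to be exposed to the chosen dose (Section 3.1.2.1). If a patient who could not be given the full activity counts as evidence that it is tolerated, the error runs toward too high a dose.

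**Working it through.** The protocol gives no target DLT rate and no operating characteristics, so there is no figure of its own to reproduce. The check traces patients through the rules.

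**1. Platelet example.** Assume related, non-serious Grade 3 thrombocytopenia after Dose 1, no bleeding, and no other severe related AE in the cohort.
- Recurrence item: not met. The wording can be read as needing a repeat event, or as covering an event that first appears after Dose 2. An event after Dose 1 only is a DLT on neither reading.
- Bleeding item and Grade 4 lasting >7 days: not met. SAE item: not met by assumption. Severe-AE item: not met with one patient.
- Section 3.1.5.2: withhold until Grade 0 or 1, then give 50%.
- If nothing recurs, the patient has had two doses, so the Section 3.1.4 condition is satisfied and the listed objective items give no DLT. If the other two patients are also clear, the score is 0/3 and the rule is to escalate.

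**2. Activity received.** With a the activity per dose (Table 3), the full cycle is 2a and a halved Dose 2 gives a + 0.5a = 1.5a, which is 75%.

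| Level | Full (mCi) | Dose 2 halved (mCi) |
|---|---|---|
| 1 | 100 | 75 |
| 2 | 200 | 150 |
| 3 | 300 | 225 |
| 4 | 400 | 300 |

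Level 4 with a halved Dose 2 equals the full Level 3 total.

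**3. Renal thresholds.** Section 1.3.2 predicts the kidneys as the dose-limiting organ, and Section 4.1 requires eGFR >59. For baseline B and on-study value v, Dose 2 is modified without an eGFR DLT when (v < 40 or v ≤ 0.6B) and v ≥ 30 and B − v ≤ 40.

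| Baseline B | Values v in the gap (mL/min) |
|---|---|
| 60 | 30 to <40 |
| 70 | 30 to 42 |
| 80 | 40 to 48 |
| 90 | 50 to 54 |
| 100 | 60 only |
| above 100 | none (a 40% fall exceeds 40 mL/min) |

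Example: 80 to 45 is a drop of 35 mL/min, and 35/80 = 44%. Dosing is withheld until 0.8 × 80 = 64, then resumed at 50%, and neither eGFR DLT limit is met.

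**4. The severe-AE item.** Take the workable reading, in which two affected patients both count. With 0, 1, 2 or 3 affected among the first three, this item contributes 0, 0, 2 or 3 DLTs. It never contributes exactly 1, so by itself it cannot produce the 1-of-3 step.

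**5. Illustration of item 4 (assumed inputs).** Let p be the per-patient chance of a severe related AE and c the share of lone events that another DLT item catches. Neither is in the documents. Take p = 1/3. The chance of none in three is (2/3)³ = 0.296, and of exactly one is 3 × (1/3) × (2/3)² = 0.444. Scored per patient, P(escalate) = 0.296 + 0.444 × 0.296 = 0.43. As written it is 0.43 at c = 1, 0.58 to 0.63 at c = 0.5 (second three patients pooled with the first, or not), and 0.296 + 0.444 = 0.74 at c = 0.

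**The case against.** Much of the DLT list does act at first occurrence in one patient: bleeding with Grade 3+ thrombocytopenia, prolonged Grade 4 cytopenias, Hy's Law, the hepatic-metastasis transaminase limits, prolonged fatigue, defined electrolyte events, related seizures and any related SAE. Both hepatic dose-modification triggers match DLT items. An event that prolongs the 48-hour admission is serious under Section 8.2, and a blood dyscrasia may be judged so. The Investigator's discretionary item extends to laboratory changes. SRC review and Sponsor confirmation are mandatory, dosimetry is considered, a kidney dose >23 Gy is a separate DLT, and the SRC Charter, which is not available to us, may add rules. Setting action thresholds below DLT thresholds is also a legitimate protective choice.

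All of this stands, and it narrows the gap to non-serious events outside the listed exceptions. It does not close the gap, because the remaining safeguards are matters of judgement. With no DLT reported, Section 3.1.5.1 lets escalation proceed unless the Investigator has another safety concern. The closing sentence of Section 3.1.4.1, on AEs of the specified grades, refers back to the list. Read as covering every Grade 3/4 event, it would empty the recurrence and duration conditions of meaning.

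Three stronger readings are tempting and are not supported:
- *An omitted Dose 2 is just as plainly scored DLT-free.* Sections 3.1.4 and 3.1.5.1 call for two doses, or a full cycle, in at least 3 patients, and such a patient may not supply that. Section 3.1.1.2 keeps the patient without saying how to count them. The text is unclear rather than permissive.
- *The 25% shortfall breaches the ±10% activity tolerance.* That tolerance surrounds the prescribed activity, and a 50% dose is itself prescribed by Section 3.1.5.2.
- *Escalation is far too likely, for example 74% against 43%.* That contrast needs c = 0, which the SAE and discretionary items make unrealistic, and an assumed p. At c = 1 the difference is nil.

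**Conclusion.** The gap is in the text and should be fixed. A patient with a related, non-serious toxicity after Cycle 1 Dose 1 that triggers dose modification but meets no DLT item can be given Dose 2 at 50% and still be counted as DLT-free at the full level, on 75% of its activity. The renal mismatch is a specific instance for baselines from 60 to 100 mL/min and vanishes above 100.

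This conclusion rests on the protocol's rules and arithmetic. It assumes that the event is judged non-serious, that no second patient in the cohort brings the severe-AE item into play where the event is severe, and that the Investigator does not invoke the discretionary item. The documents do not allow an estimate of how often this would happen or how far MTD or RDP2 would move; only the direction, upward, follows.

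That the severe-AE item cannot by itself yield 1 of 3 is a separate observation. Whether to score it per patient is an optional clinical choice.

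**What to change.** State in Sections 3.1.1.2 and 3.1.4.1 that a patient whose Cycle 1 Dose 2 is reduced or omitted because of study drug-related toxicity is not scored DLT-free at the assigned level. The patient counts as a DLT. The exception is toxicities the clinical team names in advance (Grade 2 thrombocytopenia is a natural example), for which the patient is non-evaluable for the DLT count and is replaced. This changes the no-replacement rule in Section 3.1.1.2 for the named cases only, settles the omitted-dose case, and covers the renal mismatch without touching the eGFR thresholds.

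Optionally, score the severe related AE item per patient, with named exceptions so that the existing duration and bleeding limits stand, and keep the two-patient count as the temporary stop in Section 3.1.5.1.

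The cost is amendment wording and an occasional extra expansion or replacement. Four levels of 3 plus the final 3 patients make 15, so the maximum of 18 (Section 9.2.4) leaves room for one expansion or three replacements. Beyond that the cap would need raising. As an illustration, assume the same per-patient DLT chance p at every level. A cleared level needed an expansion with probability r = l/(1 + l), where l = 3p(1 − p)². The chance of two or more expansions over four cleared levels is 1 − (1 − r)⁴ − 4r(1 − r)³. This is 7% at p = 0.05, 17% at 0.10 and 31% at 0.20.
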